For time to event such as time to first transfusion, or time to first major clinical event (eg, major adverse cardiovascular events (MACE), all-cause mortality), time to event is derived from the randomization date to the date of specific event. Subjects that do not experience the event will be censored. For time to event analysis using the on-treatment approach, the censoring date is the last dose date + 3 months (84 days) or the end of study date, whichever is earlier. For time to event analysis using the on-study approach, the censoring date is the end of study date.

Context surrounding RBC Transfusion

Clinical context surrounding RBC transfusion will be collected for each RBC transfusion event, and will be reviewed by an independent Clinical Endpoint Committee (CEC). The clinical context includes the primary reason for the transfusion event, the transfusion setting (eg, dialysis center, intensive care unit, emergency department), Hb at the time of the first transfusion of the transfusion event, clinical events (eg, bleeding, surgery), symptoms and vital signs of concerns.

Total number of units of RBC transfused

The total number of units of RBC transfused using the on-treatment approach is the sum of RBC units transfused between the randomization date and the earlier date of the last dose date + 3 months (84 days) and the end of study date. The total number of units of RBC transfused using the on-study approach is the sum of RBC units transfused between the randomization date and the end of study date.

Number of Days Hospitalized

This is the total number of days of hospitalization between the randomization date and earlier of the date of last IP + 3 months (84 days) and the end of study date for the on-treatment approach; between the randomization date and the end of study date for the on-study approach. Duration of each hospitalization stay is calculated as day of discharge - day of admission + 1. Hospitalizations with identical admission and discharge days will be counted as a hospitalization with duration of 1 day.

Area under the Curve (AUC) Calculation

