9.3.3 Handling of Incomplete Dates

Adverse events with a valid answer to the question "Did event start before first dose of investigational product?" on eCRF can be well defined based on the answer regardless of dates being completely or partially missing. Adverse events for which the start date is entirely missing will be counted as occurring on the date of first investigational product

administered. Adverse events with a partially missing start date that is conclusively prior to the date of first investigational product administered will be considered pre-treatment adverse events and excluded from safety analyses. All other partially missing adverse event dates will be handled as described below, with the reference date being the date of first investigational product administered:

- If the adverse event year is available and the day and month are missing, the day and month will be set to the 1st of January of the onset year.
- If the year and month are available and the day is missing, the day will be set to the 1st of the onset month.
- If the day and month are available and the year is missing, the year will be set to the year of the reference date.
- If the year and day are available and the month is missing, the month will be set to January of the onset year
- If the resulting date is prior to the reference date, the date will be reset to the reference date.
- If the imputed adverse event end date is prior to the imputed adverse event start date, the imputed end date will be reset to the imputed start date.

Concomitant medication with completely or partially missing dates will be queried. If after the query is resolved, the date is still incomplete with year only or year and month only, the concomitant medication start date will be imputed using the algorithm above, with the reference date being the randomization date.

All missing and partially missing onset dates of time-to-event outcomes will be queried. If after the query is resolved, the event onset date is still incomplete, this date will be imputed using the algorithm above with the reference date being the randomization date. Partial/missing death date and missing fatal AE end date will be imputed to be the last known date on study, or the imputed date as defined above, whichever is later.

Medical history partial/missing dates will be imputed using the algorithm above, with the reference date being one day prior to the randomization date.

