Hospitalization and transfusion partial/missing dates will be imputed using the above algorithm as well with the reference date being randomization date.

No other date imputation will be done.

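### SAP 9.3.3 imputes incomplete hospital discharge dates with a rule written for onset dates, so the affected stays are usually shortened, often to one day

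*SAP*

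**What the plan says.** SAP 9.3.3 sets out its date algorithm for adverse events.

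- Day missing: "If the year and month are available and the day is missing, the day will be set to the 1st of the onset month".
- Day and month missing: "the day and month will be set to the 1st of January of the onset year".
- Year missing: "If the day and month are available and the year is missing, the year will be set to the year of the reference date".
- Floor: "If the resulting date is prior to the reference date, the date will be reset to the reference date".
- Order of dates: an adverse event whose imputed end falls before its start has the end moved to the start.

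Hospital dates enter by reference: "Hospitalization and transfusion partial/missing dates will be imputed using the above algorithm as well with the reference date being randomization date". The section then rules out any further date imputation. For a date that is wholly missing there is a rule for adverse event starts only: "Adverse events for which the start date is entirely missing will be counted as occurring on the date of first investigational product" administration.

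On length of stay, SAP 6.3 says: "Duration of each hospitalization stay is calculated as day of discharge - day of admission + 1". A stay that begins and ends on the same day counts as 1 day. Number of days hospitalized is an exploratory endpoint (SAP 4.4) serving the exploratory objective on duration of hospitalization (SAP 2.4). SAP 10.5.3 summarizes it by arm with the on-treatment approach, and repeats it with the on-study approach as a sensitivity analysis.

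**The concern.** Each branch of the algorithm leans to an early date. That is a usual choice for an onset. For the end of a stay it removes days, and the hospitalization sentence does not limit the rule to admission.

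Other parts of SAP 9.3.3 are more careful. For concomitant medications the algorithm is confined to the start date, and for time-to-event outcomes to the onset date. For a death date or a missing end date of a fatal adverse event, the SAP takes the later of the imputed date and the last known date. Discharge has neither safeguard.

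Incomplete discharge dates are plausible. Protocol 8.1 allows follow-up by telephone or mail, through family, or through other physicians, and a stay may still be ongoing when the subject leaves the study. Because the on-treatment and on-study summaries use the same imputed dates, the planned sensitivity analysis would not show the problem.

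**Working it through.** The plan gives no figure to reproduce here, so the check applies its rules to example dates.

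**Inputs.** From SAP 9.3.3: the imputation rules and the reset of an end date that precedes the start. From SAP 6.3: length = discharge − admission + 1, which gives 1 for a same-day stay, as the SAP says. Assumed: randomization on 10 May 2013.

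**Single stays, each truly 8 days**

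| Stay | Missing part | Imputed date(s) | Length with reset |
|---|---|---|---|
| 12–19 Sep 2013 | discharge day | discharge 1 Sep | 1 |
| 12–19 Sep 2013 | discharge day and month | discharge 10 May (floor) | 1 |
| 12–19 Sep 2013 | discharge year | discharge 19 Sep 2013 | 8 (correct) |
| 12–19 Sep 2014 | discharge year | discharge 19 Sep 2013 | 1 |
| 28 Sep–5 Oct 2013 | discharge day | discharge 1 Oct | 4 |
| 12–19 Sep 2013 | admission day | admission 1 Sep | 19 |
| 28 Sep–5 Oct 2013 | both days | 1 Sep to 1 Oct | 31 |

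The first five rows have a known admission date, and none is overstated. The last two have an incomplete admission date, and both are overstated.

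**Discharge day missing, admission known.** Take a true length L (here up to 21 days) and admissions spread evenly over 365 days. An admission k days before the 1st of a month (k = 1 to L − 1, in each of 12 months) leads to a stay that crosses the month end, and its imputed length is k + 1. All other stays are reset to 1 day. Hence:

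- share recorded as 1 day = 1 − 12(L − 1)/365
- mean recorded length = 1 + (12/365) × L(L − 1)/2
- share recorded correctly (discharge truly on the 1st) = 12/365 = 3.3%

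| True length | Recorded as 1 day | Mean recorded length |
|---|---|---|
| 5 | 87% | 1.3 |
| 8 | 77% | 1.9 |
| 10 | 70% | 2.5 |
| 14 | 57% | 4.0 |
| 21 | 34% | 7.9 |

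For L = 8: 1 − 84/365 = 77%, and 1 + (12/365) × 28 = 1.9.

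**Effect on total days, illustration only.** Let a fraction f of stays lack the discharge day, with true length L and mean recorded length m, and let all other stays average 7 days. The share of days lost is f(L − m)/((1 − f) × 7 + fL). The documents give none of f, L or the 7 days.

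- L = 7, m = 1 + (12/365) × 21 = 1.69: f = 2% gives 0.02 × 5.31/7 = 1.5%; f = 5% gives 3.8%.
- L = 21, m = 7.90: f = 2% gives 0.262/7.28 = 3.6%; f = 5% gives 0.655/7.70 = 8.5%.

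These figures take all admission dates as known. Incomplete admission dates would offset part of the loss or reverse it.

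**The case against.** A reader might infer more than the text supports, in four ways.

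1. *Negative lengths of stay.* Without the reset, the 12–19 September stay would be 1 − 12 + 1 = −10 days. The reset is worded for adverse events, but so is the rest of the algorithm. Bringing the algorithm in by reference naturally brings the reset too, and the result is 1 day. The ambiguity justifies clearer wording, not a claim of negative durations.
2. *A bias that always flatters the result.* The same rule moves incomplete admission dates earlier and lengthens those stays: 19 or 31 days against a true 8 in the examples. Nothing in the documents says that the arms would differ, and the study is blinded.
3. *Every missing discharge date goes to randomization.* No bullet covers a wholly missing hospital date; that reading rests on analogy with adverse event starts. For a stay still ongoing, SAP 6.3 counts days between randomization and the end of the evaluation period, so it can be read as counted up to that boundary.
4. *A larger loss of days.* With L = 21 and f = 5%, a loss of 13.0% (0.05 × 20/7.70) requires every affected stay to be cut to 1 day. With only the day missing, 34% are.

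It is also fair to say that SAP 9.3.1 promises every effort to complete dates before database lock, so only residual records are affected, and that the endpoint is exploratory and descriptive. These objections limit the size and direction of the problem. They do not supply a discharge rule.

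**Conclusion.** The point holds as a defect of the stated rule for discharge dates. With a known admission date the rule never overstates a stay and usually understates it. If only the day is missing, it is right about 3% of the time, and 34% to 87% of stays between 21 and 5 days long are recorded as 1 day. This assumes that admissions are spread evenly over the year and that the reset applies.

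The net effect on days hospitalized cannot be sized, because the documents do not say how many dates will be incomplete and because incomplete admission dates act in the other direction. No difference between arms can be shown. The primary, secondary and adjudicated safety endpoints do not use length of stay. This is a small but clear error, worth correcting before database lock.

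**What to change.** In SAP 9.3.3:

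- Use the existing algorithm for admission dates only.
- Impute a partial discharge date to the latest possible date in the known month or year, capped at the earliest of next admission, death and end of study.
- For a stay recorded as ongoing, count days through the end of the evaluation window.
- For a wholly missing discharge date on a stay not recorded as ongoing, use a pre-specified value, such as the median length of stay pooled over both arms and fixed while blinded, with the same caps. Neither randomization nor end of study is a sound default. For an admission on Study Day 400, end of study at the planned Day 701 would give 701 − 400 + 1 = 302 days.
- State that discharge cannot precede admission.
- Report the number of imputed stays by arm, and repeat the summary without them.

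The change costs some SAP wording and a little programming. Its downside is overstatement. The 12–19 September stay with the discharge day unknown would run to 30 September: 30 − 12 + 1 = 19 days against a true 8, a larger error than the present 1 day. When only the day is missing the excess can reach about a month, and for year-only dates more. The latest-date rule therefore acts as an upper bound, and the repeat summary is an essential part of the change. If a central value is preferred for partial dates, the same pooled median confined to the known month or year is an alternative.

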9.4 Detection of Bias

This study has been designed to minimize potential bias by the use of stratified randomization of subjects into treatment groups and the use of blinding. Other factors that may bias the results of the study include:

- Important protocol deviations
- Inadvertent blind breaking before database lock and formal unblinding
- Investigational product dosing compliance
- The timing of, and reasons for, early withdrawal from treatment and from study

The occurrence of these factors will be assessed. Important protocol deviations will be listed and/or tabulated in the clinical study report (CSR). If necessary, the occurrence of other factors will be tabulated.

Any breaking of the blind for individual subjects prior to formal unblinding of the study will be documented in the CSR. The impact of such unblinding on the results observed will be assessed. Data such as the timing and reason for unblinding from subjects whose treatment assignments are unblinded prior to formal unblinding will be examined.

The timing of and reasons for early withdrawal from treatment and from study will be tabulated.

Additional sensitivity analyses may be included to assess the impact of the biases on the primary endpoint. If any sensitivity analyses are required to evaluate potential biases in the study's conclusions, then the sources of the potential biases and results of the sensitivity analyses will be documented in the CSR.

9.5 Outliers

Various methods, including univariate summaries, histograms, scatter plots, box plots, and line graphs, may be used to identify outliers in key safety and efficacy variables. Extreme data points will be identified during the blinded review of the data prior to database lock. Such data points will be reviewed with clinical data management to ensure accuracy. The primary analyses will include outliers in the data. Sensitivity analyses may be performed if extreme outliers for a variable are observed.

9.6 Distributional Characteristics

Statistical assumptions for the primary endpoint method of analysis will be assessed. If the assumptions for the primary analysis are not met, then nonparametric methods will be utilized. The use of alternative methods will be fully justified in the CSR.

9.7 Validation of Statistical Analyses

Programs will be developed and maintained, and output will be verified in accordance with current risk-based quality control procedures.

Tables, figures and listings will be produced with validated standard macro programs where standard macros can produce the specified outputs.

The production environment for statistical analyses consists of Amgen-supported versions of statistical analysis software, for example the SAS System and S-plus.

10. STATISTICAL METHODS OF ANALYSIS

10.1 General Principles

Descriptive statistics will be presented for all endpoints by treatment group. For continuous variables, these include number of observations, mean, standard error (SE) and/or standard deviation (SD), median, 25th percentile (Q1), 75th percentile (Q3), minimum and maximum. For categorical variables, the frequency and percentage are presented. For time to event endpoints: Kaplan-Meier curves, Kaplan-Meier percentiles, the number of subjects censored, and the number of subjects with events will be summarized. Confidence intervals will be constructed as 2-sided at the 95% level. Summaries of laboratory data, Hb and dose related parameters, and vital signs will be completed using the full analysis set, limited to measurements obtained while the subject is receiving the investigational product.

For variables that are summarized over time, the actual visit for a subject may not exactly coincide with their targeted scheduling. The visit windows defined in [Appendix A](#) will be used to assign evaluations to a most appropriate nominal visit for analysis and summarization.

10.2 Subject Accountability

The number of subjects screened, randomized, receiving IP, completing the IP and completing the study will be summarized by randomized treatment group. The date of first subject enrolled, the date of early study termination (if applicable), the date the last subject was enrolled, and date of the last subject completed follow-up will be described in a summary table.

Reasons for study discontinuation and IP discontinuation will be tabulated separately by randomized treatment group. In addition, a figure of the cumulative distribution will depict subject IP discontinuation over time by randomized treatment group, with the reasons for ending IP noted.

10.3 Important Protocol Deviations

Important Protocol Deviations (IPDs) categories are defined by the study team before the first subject's first visit and updated during the IPD reviews throughout the study prior to database lock. These definitions of IPD categories, sub-category codes and descriptions will be used during the course of the study. The final IPD list is used to produce the Summary of IPDs table (see [Section 12.1](#)) and the List of Subjects with IPDs (see [Section 12.2](#)).

10.4 Demographic and Baseline Characteristics

All baseline tables will be summarized by randomized treatment group. Baseline tables will include the following: demographic, medical history, laboratory parameters, vital signs, and baseline characteristics including weight, height, BMI, stratification factors, ECG (normal or abnormal), use of selected concomitant medications such as iron therapies and prior erythropoiesis stimulating agents. These baseline characteristics will be summarized for all randomized subjects, the full analysis set, and the completer set. In addition, baseline characteristics will be summarized for the initial Hb response analysis set by the initial Hb response subgroup.

10.5 Efficacy Analyses

The stratification factors from IVRS will be used for the analyses. Both the stratification factors and subgroups defined in [Section 6.2](#) will be considered for subgroup analyses. Additional subgroup analyses may be performed if other prognostic factors emerge in this study or in this population.

10.5.1 Analyses of Primary Efficacy Endpoint(s)

The primary analysis of the primary endpoint will be conducted using the full analysis set. The evaluation period will begin from the date of randomization, and subjects will be censored at the last dose of investigational product plus 3 months or end of study, whichever is earlier (on-treatment approach). For the primary endpoint, the proportion of subjects in each treatment group receiving at least 1 RBC transfusion during the evaluation period will be presented with 2-sided 95% CIs. The difference in proportions between treatment groups will be described with 2-sided 95% CIs. Confidence intervals

will be derived using normal approximation. The relative risk ratio and its 95% CI will be described using the Cochran-Mantel-Haenszel statistic controlling for the stratification factors.

The primary analysis will be repeated by subgroups of stratification factors used at randomization, and also by subgroups of age, gender, race, baseline Hb concentrations, baseline eGFR and diabetes at baseline.

Sensitivity analyses of the primary endpoint will be repeated using:

- All randomized subjects with the evaluation period beginning at the date of randomization and subjects will be censored at the end of study date (on-study approach).
- Completer analysis set with the evaluation period between the date of randomization and the end of study date

Sensitivity analyses will be performed to assess the impact of potential differential follow up on the primary endpoint. Exposure-adjusted subject incidence of receiving at least 1 RBC transfusion will be calculated with 95% CI using Chi-square approximation to the Poisson distribution for both on-treatment and on-study approaches.

The reason for IP discontinuation will be reviewed to evaluate its relationship and potential impact on the primary endpoint. Time to first RBC transfusion or discontinuing IP due to lack of efficacy using the on-treatment approach will be analyzed by each treatment group with Kaplan-Meier curves, Kaplan-Meier percentiles and estimates at 6, 12, 18, and 24 months, the number of subjects censored, and the number of subjects transfused or discontinuing IP due to lack of efficacy. A supportive analysis will be performed using Cox proportional hazards model (Cox, 1972) stratified by the stratification factors used at randomization to evaluate the difference between the treatment groups. The hazard ratio and its corresponding 95% CI will be estimated.

Other sensitivity analyses may be performed as appropriate.

Additional transfusion related information collected will be summarized descriptively by treatment group using both on-treatment approach and on-study approach. These include the transfusion setting, and the clinical context surrounding transfusions. These summaries will be transfusion event incidence instead of subject incidence.

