10.1.3 Subgroups and Covariates

Subgroups and covariates to be considered include the stratification factors used at randomization, and the following baseline factors: age, sex, race, baseline Hb concentration and baseline eGFR. Subgroups are defined as

- Age: < 65, ≥ 65 and < 75, ≥ 75 years
- Gender: Female, Male
- Race: White, Black, Other
- Baseline Hb concentrations: <9.0, 9.0 – < 9.5, 9.5 – < 10.0 g/dL
- Baseline eGFR: < 30.0, ≥ 30.0 mL/min/1.73m²

Additional analyses may be performed if other prognostic factors emerge in this study or in this population.

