10.5.2 Analysis of Key Study Endpoints

10.5.2.1 Efficacy Endpoints

The primary analysis of the primary endpoint will be conducted using the full analysis set. The evaluation period will begin from the date of randomization and subjects will be censored at the last dose of investigational product plus 3 months or end of study, whichever is earlier (on-treatment approach). For the primary endpoint, the proportion of subjects in each treatment group receiving at least 1 RBC transfusion during the evaluation period will be presented with 2-sided 95% CIs. The difference in proportions between treatment groups and the relative risk ratio will be described with 2-sided 95% CIs. Confidence intervals will be derived using normal approximation.

The primary analysis will be repeated by subgroups of stratification factors used at randomization, and also by subgroups of age, gender, race, baseline Hb concentrations and baseline eGFR.

Sensitivity analyses of the primary endpoint will be repeated using all randomized subjects with the evaluation period beginning at the date of randomization and subjects will be censored at the end of study (on-study approach).

Sensitivity analyses will be performed to assess the impact of potential differential follow up on the primary endpoint. Exposure-adjusted subject incidence of receiving at least 1 RBC transfusion will be calculated with 95% CI using Chi-square approximation to the Poisson distribution for both on-treatment and on-study approaches. Other sensitivity analyses, such as completer analyses for investigational product and study, may be performed as appropriate.

The reason for investigational product discontinuation will be reviewed to evaluate its relationship and potential impact on the primary endpoint. Additional transfusion related information collected will be summarized descriptively by treatment group using both on treatment approach and on study approach. These include the transfusion setting and clinical context surrounding transfusions. These summaries will be of transfusion event incidence instead of subject incidence.

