5. HYPOTHESES AND/OR ESTIMATION

The incidence of RBC transfusions in each treatment group (Hb-based titration group and fixed dose group) and their difference will be estimated, and no formal hypothesis will be tested. The width of the 95% CI of the transfusion incidence rate is expected to be < 10% (ie, $\pm 5\%$ around the point estimate) in each group and the width of the 95% CI of the difference in transfusion incidence rates is expected to be < 14% (ie, $\pm 7\%$ around the point estimate). The efficacy and safety of each treatment group will be described, as these aspects will assist in the determination of a preferred dosing regimen.

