10.5.2 Analyses of Secondary Efficacy Endpoint(s)

Total number of units of RBC transfused per subject will be described for each treatment group, and will be analyzed using a negative binomial regression model which will

include the stratification factors used at randomization. As a sensitivity analysis, exposure adjusted event incidence of total number of units RBC transfused will be presented with 95% CI using Chi-square approximation to the Poisson distribution. These analyses will be performed using both on-treatment approach with the full analysis set and on-study approach with all randomized subjects.

Time to first RBC transfusion will be analyzed using both on-treatment approach with the full analysis set and on-study approach with all randomized subjects. It will be analyzed by each treatment group with Kaplan-Meier curves, Kaplan-Meier percentiles and estimates at 6, 12, 18, and 24 months, the number of subjects censored, and the number of subjects transfused. A supportive analysis will be performed using Cox proportional hazards model (Cox, 1972) stratified by the stratification factors used at randomization to evaluate the difference between the treatment groups. The hazard ratio and its corresponding 95% CI will be estimated.

Average achieved Hb concentration while receiving investigational product will be described as average Hb using the area under the curve (AUC) method. The median of the difference in achieved Hb concentration (Hodges–Lehmann estimate) between treatment groups will be calculated and 2-sided 95% confidence limits will be derived by using a nonparametric Wilcoxon rank-sum statistic (Hollander and Wolfe, 1973). As a sensitivity analysis, the above analyses will be repeated excluding Hb concentrations measured within 3 months (84 days) from an RBC transfusion.

Cumulative doses of darbepoetin alfa adjusted for investigation product exposure time (eg, average cumulative darbepoetin alfa dose per 4 week) will also be summarized, and the median of the difference (Hodges–Lehmann estimate) between treatment groups will be calculated and 2-sided 95% confidence limits will be derived by using a nonparametric Wilcoxon rank-sum statistic.

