11. CHANGES FROM PROTOCOL-SPECIFIED ANALYSES

There are no changes to the protocol-specified analyses.

12. LIST OF PLANNED TABLES, FIGURES AND LISTINGS [TFLs]

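### Optional improvement: SAP 10.5.1 leaves the primary difference in proportions unstratified; a Mantel-Haenszel difference would give on average the same or a slightly narrower 95% interval

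*SAP*

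**What the plan says.** SAP 10.5.1 gives each group's proportion a 95% interval and then states: "The difference in proportions between treatment groups will be described with 2-sided 95% CIs". These intervals are to come from the normal approximation, and no strata are mentioned. The relative risk follows, with a different treatment: "The relative risk ratio and its 95% CI will be described using the Cochran-Mantel-Haenszel statistic controlling for the stratification factors".

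The other between-group transfusion analyses also use the strata. The Cox model for transfusion or stopping for lack of efficacy is "stratified by the stratification factors used at randomization to evaluate the difference between the treatment groups", and SAP 10.5.2 specifies the same for time to first transfusion. The negative binomial model for units transfused will "include the stratification factors used at randomization".

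The factors are transfusion in the 12 months before randomisation and practice setting of the site (Protocol 5.2), which form four strata. Protocol 10.1.3 says: "Subgroups and covariates to be considered include the stratification factors used at randomization". SAP 10.5 opens with a general statement that the IVRS values of these factors feed the analyses.

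Protocol 10.5.2.1 treats both measures alike: "The difference in proportions between treatment groups and the relative risk ratio will be described with 2-sided 95% CIs". It uses the normal approximation and mentions strata for neither. SAP Section 11 nevertheless states: "There are no changes to the protocol-specified analyses".

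**The concern.** SAP 5 says of the two groups' incidences that "their difference will be estimated, and no formal hypothesis will be tested". The interval for the difference is therefore the main comparative result, and the trial is sized on interval width. Yet the method for this contrast leaves the design strata out, while the neighbouring transfusion contrasts use them.

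One factor is prior transfusion and the endpoint is transfusion, so some prognostic value is plausible, although the documents do not show it. If the strata do predict the outcome, the unstratified interval ignores balance that the randomisation has already secured. It is then a little wider than it needs to be and covers slightly more than 95%. What is at stake is a small amount of precision, and consistency between the difference and the relative risk shown beside it. No analysis fails if the plan is left as it is.

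**Working it through.** **1. Inputs.** From SAP 3.2: 25% risk in both groups; 300 per group, raised to 375 for 20% drop-out; target widths of at most 10 points (one group) and 14 points (difference); normal approximation. From Protocol 5.2: 1:1 allocation. z = 1.96. Stratum shares and stratum risks are not in the documents and are assumed throughout.

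**2. The plan's own figures.** 300/0.8 = 375.
- One group, width 2 × 1.96 × √(0.25 × 0.75/n): 9.80 points at 300 and 8.77 at 375.
- Difference, half-width 1.96 × √(2 × 0.25 × 0.75/n): 6.93 points at 300 (width 13.86) and 6.20 at 375 (width 12.40).

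Both targets are met and the stated sample size is reproduced.

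**3. Effect of stratifying.** The Mantel-Haenszel weight of stratum k is n1k × n0k/(n1k + n0k). With 1:1 balance within strata this is proportional to stratum size. The variance is then the crude variance times r = Σ s_k p_k(1 − p_k)/[p(1 − p)], where s_k is the stratum share and p = 0.25. The half-width is multiplied by √r.

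Example with an 11% stratum at 50% risk: the risk elsewhere is (0.25 − 0.055)/0.89 = 21.9%. Then r = (0.11 × 0.25 + 0.89 × 0.219 × 0.781)/0.1875 = 0.959, and 6.20 × √0.959 = 6.07.

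| Share | Risk in stratum | Risk elsewhere | r | Half-width at 375 (points) | Change |
|---|---|---|---|---|---|
| any | 25% | 25% | 1.000 | 6.20 | 0% |
| 10% | 35% | 23.9% | 0.994 | 6.18 | −0.3% |
| 10% | 45% | 22.8% | 0.976 | 6.12 | −1.2% |
| 11% | 50% | 21.9% | 0.959 | 6.07 | −2.1% |

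At 300 per group the last case takes 6.93 to 6.79. A second calculation let prior transfusion be present in 10-30% of subjects, with practice setting either neutral or a 1.3-fold factor. If prior transfusion doubles the risk, the full width at 375 is 12.11-12.24 (1.3-2.3% narrower). If it triples the risk, the width is 11.66-11.87 (4.3-5.9% narrower).

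**4. Coverage and single-trial behaviour.** This was simulated at 375 per group with the Sato variance, assuming 20% non-nephrology sites and blocks of 4.
- Mantel-Haenszel coverage was 94.8-95.0%. Crude coverage was 94.9% with non-prognostic strata and 95.4% at 11%/50%.
- With non-prognostic strata both mean half-widths were 6.19.
- In single trials the stratified interval was the wider one about 51% of the time with non-prognostic strata and 22-23% of the time at 10%/35%. The excess was about 1%, and no more than 1.5% in any blocked run.
- The two point estimates differed on average by less than 0.1 point.

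**5. Subgroups.** With an 11% stratum and unblocked allocation, at least one stratum had an empty arm in 47% of replicates at 60 per arm and in 80% at 30 per arm. At 30 per arm with non-prognostic strata, the stratified half-width was 22.15 against 21.66 crude, with coverage of 93.9% against 94.2%. Stratifying does not help there.

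**The case against.** The strongest objection is that this is a preference. The unstratified interval is valid and meets the only precision criterion set for the difference. A gain of 0.02-0.13 point in half-width will not change a conclusion, and Protocol 2.3 rests the choice of regimen on several considerations. That stands, and it is why the point is optional.

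A second objection is that the plan may already intend stratification. A Mantel-Haenszel interval is also a normal approximation, SAP 10.5 has its general statement about IVRS factors, and the primary table entry in SAP 12.1 can be read as applying the Cochran-Mantel-Haenszel control to both measures. The code in Appendix B is blacked out and cannot settle it. This shows loose wording, but SAP 10.5.1 attaches the adjustment to the relative risk only and SAP 3.2 sizes the trial on the unstratified formula. Unstratified remains the governing reading.

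A third objection is that the change has a price. A stratified difference need not equal the subtraction of the two displayed proportions, it replaces a protocol-specified method, and the subgroup repeats would use a different estimator. This stands, and it is why the unstratified difference should be kept as supportive.

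A reader might infer that stratifying always gives the same or a narrower interval. That is exact only with 1:1 balance in every stratum and a variance using divisor n. With the Sato variance a single trial can go slightly the other way.

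A reader might also infer a large gain. A 30% stratum at 50% risk against 14% elsewhere would give 5.74 points, 7.4% narrower, but nothing in the documents supports those values. The only related share is 11.1%, from a different cited study over 6 months (Protocol 2.3). Protocol 4.2 also excludes subjects transfused within 8 weeks of screening or during screening.

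**Conclusion.** This is a free improvement, optional, and not an error. A stratified difference would give on average the same or a slightly narrower 95% interval: about 0-2% narrower for a stratum of about 10% with risk up to 50%. Gains beyond that need roughly a tripled risk, or prior transfusion that is both common and strongly prognostic. In one trial with weak strata the interval may be about 1% wider. All of this rests on assumed shares, risks and block size, with 25% risk overall.

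It would be wrong to conclude that the planned interval is invalid or misses its target. It is at worst slightly conservative, and at the plan's 25% its width is below 14 points at both 375 and 300 per group.

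**What to change.** In SAP 10.5.1, specify the overall primary difference as the Mantel-Haenszel risk difference over the two IVRS stratification factors, naming the Mantel-Haenszel weights and the Sato variance, with a two-sided 95% interval. Keep the unstratified difference and its interval as supportive, because it matches the displayed proportions, and use it in the subgroup repeats, where strata can be sparse. Reword the primary table entry in SAP 12.1 to say which measure is stratified and how.

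In SAP Section 11, record both this change and the Cochran-Mantel-Haenszel adjustment of the relative risk, since neither is in Protocol 10.5.2.1.

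The cost is one or two sentences in SAP 10.5.1, one table edit, one Section 11 entry and a standard procedure option, all settled before unblinding. No extra data or subjects are needed.
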